The following doses of P10s-PADRE and MONTANIDE™ ISA 51 VG vaccine will be administered to subjects subcutaneously in rotating injection sites in the abdomen or extremities. Subjects will receive up to 2.0 ml subcutaneous (SC) injections of the vaccine on 5 separate occasions (Weeks 1, 2, 3, 7, and 19).

- **500 µg P10s-PADRE/ MONTANIDE™ ISA 51 VG Vaccine Dose preparation:** The UAMS pharmacist will prepare the vaccine dose following the manufacturer's instructions. (See CMC section of the IND).
- **300 µg P10s-PADRE/ MONTANIDE™ ISA 51 VG Vaccine Dose preparation:** The UAMS pharmacist will prepare the vaccine dose following the manufacturer's instructions. (See CMC section of the IND).

d. DTH Preparation:

- Trichophyton: per insert instructions.
- Candida: per insert instructions.
- 100 µg P10s-PADRE: The UAMS pharmacist will prepare the DTH dose following the manufacturer's instructions. (See CMC section of the IND).

e. Dosing Administration:

The DTH dose will be injected SC on the back of the patient by clinic staff.

f. Label Information: The vaccine drug supply (both P10s-PADRE and MONTANIDE™ ISA 51 VG will be labeled with the following statement: "Caution: New Drug – Limited by Federal Law to Investigational Use".

g. Agent Ordering: All drug study supplies (P10s-PADRE vials and MONTANIDE™ ISA 51 VG vials) will be sent to the attention of the UAMS Research Pharmacy staff. Initial drug supply order will be placed by primary investigator and both P10s-PADRE vials and MONTANIDE™ ISA 51 VG vials will be shipped directly to UAMS Research Pharmacy, [name].

h. Agent Accountability: P10s-PADRE and MONTANIDE™ ISA 51 VG will be stored in the UAMS Pharmacy under the supervision of the research pharmacist who will be responsible

for maintaining the supply according to the manufacturer's specifications, dispensing the drug for administration and maintaining all accountability logs. Standard NCI accountability logs will be used.

7. Treatment Plan

- a. On-study Evaluation:** After signing the IRB-approved informed consent form, research participants will be assigned to a cohort at the time of consent by a clinical research associate (CRA) in the Cancer Clinical Trials Office (CCTO) in the Cancer Institute. All research participants will receive the Mimotope P10s-PADRE/ MONTANIDE™ ISA 51 VG vaccine via subcutaneous (SC) injection following the schedule on the Study Calendar in Section 9.

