- Toxicity evaluations using the NCI CTCAE (National Cancer Institute Common Terminology Criteria for Adverse Events) Version 4.0. Toxicities to be assessed are the laboratory parameters listed in the study calendar, as well as any sign or symptom found during the history and physical examination not noted at prestudy or on the baseline evaluation. Special attention will be paid to signs and symptoms related to injection reactions, injection site reactions or symptoms or laboratory findings indicating autoimmune toxicities.
- Concomitant medications will be collected from registration to end of treatment.
- DTH Skin Test to test the subjects' immunocompetency. Trichophyton Antigen and the Candida antigen will be administered intradermally (id) as control antigens at separate locations on the subject's back, and the resulting induration will be read 48– 72 hours later; 100 µg Mimotope P10s-PADRE will be given id alongside the control antigens to determine subjects' DTH response to vaccine.
- Study lab samples. Up to 40 mLs of blood will be collected in red and purple tubes for circulating tumor cell evaluation, TACA (tumor associated carbohydrate antigens) assessment, and immune effector assays.

48 – 72 hours later

- DTH Skin test reading.

Week 19

- Administration of the P10s-PADRE/MONTANIDE™ ISA 51 VG vaccine. The vaccine will be administered subcutaneously (SC) by nurses in the Infusion Center at the Cancer Institute.
- Post vaccine administration, the following vital signs will be monitored every 15 (+/- 5 minutes) minutes for one hour: blood pressure, temperature, and pulse.
- Complete medical history and physical examination
- Complete blood count with differential
- Other blood tests include:
 - Collection of serum samples used to measure the immune response to the vaccine. If vaccine is given on these days, the study labs will be drawn before the vaccine is administered.
 - SGOT (Serum glutamic-oxaloacetic transaminase)
 - Alkaline Phosphatase Level
 - LDH (lactate dehydrogenase)
 - GGT (gamma-glutamyl transferase)
 - Creatinine
 - Calcium
 - Albumin
 - Amylase
 - TSH (thyroid stimulating hormone)
 - T₄
 - ANA (Anti-nuclear antibody)
 - PT/PTT
 - Bilirubin

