- Study lab samples. Up to 40 mLs of blood will be collected in red and purple tubes for circulating tumor cell evaluation, TACA (tumor associated carbohydrate antigens) assessment, and immune effector assays.
- CTC (circulating tumor cells) response to the vaccine will be measured in serum samples drawn to determine the presences of CTCs pre- and post-mimotope administration.

48 – 72 hours later

- DTH Skin test reading.

Week 24

[figure not shown]
- Complete medical history and physical examination
- Complete blood count with differential
- Other blood tests include:
 - Collection of serum samples used to measure the immune response to the vaccine. If vaccine is given on these days, the study labs will be drawn before the vaccine is administered.
 - SGOT (Serum glutamic-oxaloacetic transaminase)
 - Alkaline Phosphatase Level
 - LDH (lactate dehydrogenase)
 - GGT (gamma-glutamyl transferase)
 - Creatinine
 - Calcium
 - Albumin
 - Amylase
 - TSH (thyroid stimulating hormone)
 - T₄

- ANA (Anti-nuclear antibody)
- PT/PTT
- Bilirubin
- Toxicity evaluations using the NCI CTCAE (National Cancer Institute Common Terminology Criteria for Adverse Events) Version 4.0. Toxicities to be assessed are the laboratory parameters listed in the study calendar, as well as any sign or symptom found during the history and physical examination not noted at prestudy or on the baseline evaluation. Special attention will be paid to signs and symptoms related to injection reactions, injection site reactions or symptoms or laboratory findings indicating autoimmune toxicities.
- Concomitant medications will be collected from registration to end of treatment. Study lab samples. Up to 40 mLs of blood will be collected in red and purple tubes for circulating tumor cell evaluation, TACA (tumor associated carbohydrate antigens) assessment, and immune effector assays.

Follow up

Follow up will occur at next scheduled standard of care visit every six months for five years and then yearly until death.

- Collection of serum samples used to measure the immune response to the vaccine.
-
- e. **Prohibited Medications:** Systemic steroids are prohibited. If a subject wishing to participate in the study has been on systemic steroids, a 6-week clearing of the drug will be required prior to participation in the study.

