Subjects will receive up to 5 planned vaccine doses unless they withdraw from the study or develop a dose limiting event as stated above, at which time they will discontinue the injections and be removed from the study. There will be no dose modifications for toxicity. Special attention will be given to toxicities mediated by autoimmune mechanisms, such as colitis, thyroiditis or systemic lupus erythematosus (SLE), as well as to injection-site local reactions or allergic reactions. The NCI CTCAE Version 4.0 will be used for toxicity and SAE reporting. A copy of the CTCAE Version 4.0 can be downloaded from the Cancer Therapy Evaluation Program (CTEP) home page or viewed in **APPENDIX A**. All appropriate treatment areas have access to a copy of the CTCAE Version 4.0.

Any subject may voluntarily revoke consent and withdraw from the study at any time. A subject may be terminated early for the following conditions: (i) non-compliance, (ii) an unrelated intercurrent illness that may affect assessment or place the subject at risk for AEs or require systemic steroids, (iii) deterioration in performance status so as to make participation a hardship for the subject, (iv) for toxicity as determined by the DLT criteria, or (v) for any reason that the investigator feels it is not in the subject's best interest to continue.

- b. Benefits:** As this is the first time Mimotope P10s-PADRE will be administered to humans, there are no clearly defined benefits to subjects of this study. However, this vaccine may potentiate an immune response which could improve median progression-free survival and overall survival of cancer patients.
- c. Injury:** For DOD-funded research, participants can receive medical care at an Army hospital or clinic free of charge. If participants pay out-of-pocket for medical care elsewhere for injuries caused by this research study, they should contact the Principal Investigator. If the issue cannot be resolved, contact the U.S. Army Medical Research and Materiel Command (USAMRMC) Office of the Staff Judge Advocate (legal office) at [contact]/[name]

9. Specimen Handling

Samples will be stored in the UAMS Tissue Procurement Facility, located in room B.018 of the hospital. Cryotubes that contain specimens will be labeled with barcodes. The coded number is linked to patient identification and time of blood draw. Specimens will be stored frozen at -80°C

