⁵The DTH skin test at prestudy will test the subjects' immunocompetency. Control antigens, Trichophyton Antigen and Candida antigen, will be administered id and the resulting induration will be ready at 48 - 72 hours post injection.

⁶ The DTH skin tests on weeks 5, 9 and 21 will test the DTH response to Mimotope P10s-PADRE. Trichophyton Antigen and Candida antigen will be administered id alongside Mimotope P10s-PADRE as control antigens to assess immunocompetency. DTH skin test indurations will be read at 48 – 72 hours post injection.

⁷ Visits must occur at set time points mentioned in the study calendar (+/- 3 days) with the exception of reading the skin test which must occur 48-72 hours post administration.

⁸ Concomitant medications will be collected from registration to end of treatment.

⁹ Post vaccine administration, the following vital signs will be monitored every 15 minutes (+/- 5 minutes) for one hour: blood pressure, temperature, and pulse.

¹⁰ Follow up visits shall begin with the next scheduled standard of care appointment and then shall occur every six months for five years and then yearly until death.

11. Criteria for Evaluation

Primary Objective – Safety:

- **Determination of DLT:** See Section 8, “Risks and Toxicities to be Monitored”. Any event that meets the dose limiting criteria will be determined a dose limiting toxicity.

Secondary Objectives – Immune Response:

- **Immunological Evaluation:** Serum will be collected at the Study Lab time points indicated in the study calendar in Section 10. Samples will be collected and stored by the UAMS Cancer Institute Tissue Bank following established Tissue Bank SOPs. IgM and IgG titers to TACAs will be evaluated by ELISA on TACA adhered to plates and FACS analysis of TACA adhered to liposomes. A positive TACA-directed immune response will be defined as an anti-TACA serum antibody titer of 1:40 for a baseline pre-vaccination titer of 0 or a \geq 4-fold increase over baseline titer > 0 (1, 11). Subjects will be judged to have had an adequate immune response if they have a positive TACA-directed immune response at any one of the first five designated time points following vaccine administration (Weeks 2, 3, 4, 7 and 9). The value of a booster immunization will be determined by anti-TACA IgM and IgG titers obtained from study labs collected on week 21.

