It should be noted that the primary objective of this study is to ensure the safety of the mimotope vaccine. Because of sample size, these studies only provide a qualitative assessment of vaccine immunogenicity. However, our immunization schedule should favor the generation of antibodies (1, 11, 42). A positive TACA-directed immune response will be defined as an anti-TACA serum antibody titer of 1:40 for a baseline pre-vaccination titer of 0 or a \geq 4-fold increase for a baseline titer > 0 (1, 11). A subject will be judged to have had an adequate immune response if they have a positive TACA-directed immune response at any one of the first five indicated time points following vaccine administration on the study calendar (Section 10, Study Lab Weeks 2, 3, 4, 7 and 9). An additional immune-response endpoint will be the DTH response to Mimotope P10s-PADRE. The components of the DTH response, namely, the induration in mm across two diameters, will be tabulated by antigen (the mimotope vs. the two DTH controls) for each subject at the indicated time points on the study calendar. An induration of >5 mm in at least one diameter will be considered a positive DTH response.

b. Data Analysis Plan: Toxicity will be graded according to the NCI CTCAE Version 4.0. All toxicities observed in a study subject will be enumerated and reported in terms of type (organ affected or laboratory determination such as absolute neutrophil count), severity (by NCI Common Toxicity Criteria (CTC) and nadir or maximum values for the laboratory measures), time of onset (i.e. dose number), duration and reversibility or outcome. A toxicity meeting the dose limiting criteria as stated above will be scored as a DLT. The number and proportion of subjects in each dose cohort who suffer a DLT will be reported. The number of DLTs observed will be reported by dose cohort, both overall and also broken down by CTCAE category.

To meet the secondary objective of determining the humoral response against TACAs, the anti-TACA serum titers measured from subjects' blood samples will be collected at pre-study and on weeks 2, 3, 4, 7, and 9. IgM and IgG titers to TACAs will be evaluated by ELISA and

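### Section 12.b gives toxicity onset only as a dose number, so same-type events cannot be split into early and delayed, and skin-test reactions carry a vaccine-dose label

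*Combined protocol and SAP*

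**What the plan says.** Section 12.b (Data Analysis Plan) enumerates every toxicity, "reported in terms of type (organ affected or laboratory determination such as absolute neutrophil count"), then by severity, and then by "time of onset (i.e. dose number), duration and reversibility or outcome". The abbreviation makes dose number the definition of onset. I found no section that adds an onset day, or a time since injection, to the toxicity report.

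Section 6.c has the vaccine given "on 5 separate occasions (Weeks 1, 2, 3, 7, and 19"). Section 8 confirms the count: "Subjects will receive up to 5 planned vaccine doses unless they withdraw from the study".

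The peptide is also given outside those five doses. Footnote 6 of the Study Calendar (Section 10) states: "The DTH skin tests on weeks 5, 9 and 21 will test the DTH response to Mimotope P10s-PADRE". Section 7.d gives the amount and route, for example at Week 9: "100 µg Mimotope P10s-PADRE will be given id alongside the control antigens".

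In Section 7.d the last visit that lists a toxicity evaluation is Week 24. After that, "Follow up will occur at next scheduled standard of care visit every six months for five years and then yearly until death", and only serum collection is listed there.

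Section 8 also says which harms it is watching for: "Special attention will be given to toxicities mediated by autoimmune mechanisms, such as colitis, thyroiditis or systemic lupus erythematosus (SLE"), together with injection-site and allergic reactions.

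**The concern.** Dose number is a usable time scale when doses are evenly spaced and are the only exposure. Neither is true here. The label for dose 4 covers the day after the Week 7 injection and also Week 18, which is 11 weeks later. Someone reading the report could not tell which applied.

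The skin tests add a second difficulty. They deliver the same peptide, and Section 8.a lists allergic reaction, including anaphylaxis, among their risks. If dose number counts vaccine doses only, a reaction to the Week 9 skin test is reported under dose 4, given 14 days earlier.

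What is at stake is the description and attribution of toxicity in a first-in-human study whose primary objective is safety. Lag from exposure is one of the few pieces of evidence a small uncontrolled cohort can offer on whether an event is an acute reaction, a delayed one, or background from stage IV disease and permitted chemotherapy.

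**Working it through.** The plan states no figure on this point, so there is none to reproduce. The inputs are the vaccination weeks (Section 6.c), the skin-test weeks (Section 10, footnote 6) and the visits with a toxicity evaluation (Section 7.d: Weeks 1, 2, 3, 7, 9, 19, 21 and 24).

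**Interval lengths.** Days = 7 × (week of next dose − week of this dose). The dose 5 interval is closed at Week 24.

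**Share by days.** The documents give no background event rate. Assume a constant rate and complete ascertainment; the share is then days ÷ 161, whatever the rate.

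**Share by visits.** Instead, give each scheduled post-dose toxicity evaluation equal weight and credit it to the preceding dose. Week 1 is left out because no dose precedes it.

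| Dose | Interval (weeks) | Days | Share of 161 days | Evaluations after the dose | Share of 7 evaluations |
|---|---|---|---|---|---|
| 1 | 1–2 | 7 | 4.3% | Week 2 | 14% |
| 2 | 2–3 | 7 | 4.3% | Week 3 | 14% |
| 3 | 3–7 | 28 | 17.4% | Week 7 | 14% |
| 4 | 7–19 | 84 | 52.2% | Weeks 9, 19 | 29% |
| 5 | 19–24 | 35 | 21.7% | Weeks 21, 24 | 29% |

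Dose 4 against dose 1 is 84 ÷ 7 = 12 by days and 2 ÷ 1 = 2 by visits.

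**Sensitivity of the figure by days.**

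- *Drop-out.* With a constant hazard and a proportion p still in the study at Week 24, put r = −ln(p)/161. The share of an interval from day a to day b is (e^(−ra) − e^(−rb)) ÷ (1 − p). For p = 0.8, dose 4 has 52% and dose 1 has 4.8%, a ratio of about 10.7. For p = 0.2 they have 47% and 8.4%, a ratio of about 5.5.
- *End of reporting.* The dose 5 interval would equal that of dose 4 if toxicity reporting ran to Week 31 (7 × 12 = 84 days). Beyond that, dose 5 would be the longest.
- *Visit windows.* Section 10 allows ±3 days per visit, so one subject's interval can differ from nominal by up to 6 days.

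**Loss of lag within a label.** Under a constant rate, (84 − 14) ÷ 84 = 70 ÷ 84 = 83% of background events labelled dose 4 start more than 14 days after that dose. For doses 1 and 2 the label already limits the lag to about a week, so the loss is in intervals 3 to 5.

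**Skin tests.** Days from the preceding vaccine dose are 7 × (5 − 3) = 14, 7 × (9 − 7) = 14 and 7 × (21 − 19) = 14. Each skin test therefore falls inside an interval. At 100 µg, one test is 33% of a 300 µg vaccine dose, 20% of a 500 µg dose and 100% of a 100 µg dose.

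**DLT window.** Weeks 1 to 9 give 7 + 7 + 28 + 14 = 56 days. The shares are 12.5%, 12.5%, 50% and 25% for doses 1 to 4, so dose 4 does not dominate there.

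**The case against.** A reader might infer that a delayed autoimmune toxicity would look the same as an acute reaction to the same dose. The documents do not support that. The same sentence of Section 12.b reports type, severity, duration and outcome, so colitis, thyroiditis or lupus would differ from an injection-site reaction whatever the onset label. What remains is narrower: two events of the same type cannot be told apart by lag.

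A reader might also infer that the report will show toxicity climbing with repeated dosing. It need not. Section 12.b plans no count or rate by dose number; its named summaries are DLTs by dose cohort and by CTCAE category. Nor do the shares by days rise steadily: doses 1 and 2 are equal and dose 5 falls back to 21.7%. The 12-fold figure compares the shortest interval with the longest and assumes events are captured continuously, although no toxicity evaluation is scheduled between Weeks 9 and 19. By scheduled visits the difference is 2-fold. The imbalance is thus a conditional risk, for anyone who later tabulates by dose number.

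The decisions of the trial do not depend on the label. Tables 1 to 3 use the number of subjects with a DLT. Section 16 asks, whenever possible, for the investigator's judgment of relationship to study medication, and Section 17 bases suspension on attribution to the study drug. Section 12.c sends all collected data to the FDA, so dates are probably recoverable. All of this stands, and it limits the point to descriptive reporting. It does not put lag into the planned report.

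Finally, dose number is not defined, and Section 6 does call the skin-test injection a DTH dose. Counting vaccine doses only is still the natural reading, since Section 8 speaks of five planned vaccine doses.

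**Conclusion.** The point holds as a weakness in how toxicity is described. The only timing reported is a label covering anything from 7 to 84 days, and it gives no place to peptide skin tests that fall 14 days into three of the five intervals. Same-type events in those intervals cannot be sorted into early and delayed, and a skin-test reaction is reported under an earlier vaccine dose.

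Any count by dose number would be biased towards dose 4 relative to dose 1. The size is about 2-fold by scheduled visits and up to 12-fold by days. The upper figure rests on nominal dates, a constant event rate, complete ascertainment, no drop-out and toxicity reporting that ends at Week 24.

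It would go too far to conclude that the primary safety decision is compromised. DLT counts, escalation and the MTD are unchanged. The change is worth making because it is cheap.

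**What to change.** In Section 12.b, replace dose number as the definition of onset with four items: *onset date; number of vaccine doses received; days since the last vaccine dose; and, separately, days since the last mimotope skin test, if any*. Give subject-days at risk beside any tabulation by dose number.

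Keep the two clocks separate. A single clock from the most recent injection of either kind would restart at each skin test: an event at Week 9 plus 3 days would read day 3, although it is day 14 + 3 = 17 after dose 4. I would not impose a fixed early/late cut-off such as 7 days. The documents support none, and the intervals after doses 1 and 2 are themselves nominally 7 days, so no late category could exist there.

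The cost is two derived variables and a slightly longer safety listing. No new data should be needed, because duration is already reported and requires a start date; that onset dates are held is my inference from this. No dose, schedule, DLT definition or stopping rule changes.

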Anticipated anti-cancer impact of carbohydrate-targeted vaccines: The potential impact of vaccines that induce responses to tumor-associated carbohydrate antigens (TACAs) is demonstrated by clinical trials where patient survival significantly correlates with carbohydrate-reactive IgM levels (2). Such results suggest that TACA-targeting vaccines might have a beneficial effect on the course of malignant disease. TACA-induced responses could augment naturally occurring carbohydrate-reactive IgM antibodies that trigger apoptosis of tumor cells (3). TACAs are attractive targets because the majority of cell-surface proteins and lipids are glycosylated, and the glycosyl moiety is fundamental to the biological functions of these molecules in cancer cells (4,5). A unique advantage in targeting TACAs is that multiple proteins and lipids on the cancer cell can be modified with the same carbohydrate structure. Thus,

targeting the carbohydrate antigen broadens the spectrum of antigens recognized by the immune response, thereby lowering the risk of developing resistant tumors due to the loss of any one antigen (6). In addition, antibodies that recognize glycolipids are more apt to mediate complement-dependent cytotoxicity (CDC) and may, therefore, be more cytotoxic to tumor cells than antibodies that recognize protein antigens (7). Furthermore, preclinical studies support the hypothesis that vaccine-induced responses against TACAs might have their greatest impact in the adjuvant setting, as such responses inhibit tumor outgrowth in metastatic models (8,9).

Approaches to augment immune responses to TACA: A variety of approaches are being taken to generate responses to TACAs. Because TACAs are T-cell-independent antigens and self-antigens, conjugation to immunologic carrier proteins is perceived to be essential to recruit T-cell help in antibody generation. Conjugation does not, however, assure an increase in immunogenicity because conjugation strategies do not uniformly enhance carbohydrate immunogenicity (10,11). Furthermore, even with conjugation, the lack of induction of cellular immune responses that would amplify TACA-reactive humoral responses necessitates constant boosting with vaccine. Representative examples of carbohydrate-based conjugate vaccines in clinical development include those directed toward gangliosides (12-14), polysialic acid (15), Globo-H (16), Lewis Y (LeY) (1), and the sialosyl-TN (STn) antigen (17).

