FACS analysis. Titer will be defined as the highest serum dilution yielding an $OD_{405} \geq 0.15$, in accordance with previous studies (1) or an MFI two standard deviations higher than background. A positive TACA-directed immune response will be defined as an anti-TACA serum antibody titer of 1:40 post-vaccination when the baseline pre-vaccination titer was 0, or a ≥ 4 -fold increase in titer post-vaccination when the baseline titer was greater than 0. The number and proportion of positive TACA-directed immune responses at each time point will be reported, both overall and by dose cohort. The number and proportion of subjects with at least one positive TACA-directed immune response will also be reported, both overall and by dose cohort. Medians and quartiles of titer will also be reported at each time point for any dose cohort of size 6.

To meet the secondary objective of analyzing the DTH response, we will measure the induration in mm across two diameters at the injection sites of the mimotope and control antigens. This will be done for each study subject at all indicated time points on the study calendar. An induration of >5 mm across at least one diameter will be considered a positive DTH response to that antigen at that time point. The number of subjects who show at least one positive DTH response to mimotope during the study will be reported as the number and proportion in each dose cohort. The number of positive DTH responses to mimotope at each time point will be reported as the number and proportion in each dose cohort. Positive DTH responses to the control antigens will be summarized the same way. Additionally, the two induration measurements per injection site, as well as their product (in mm^2), will be graphed as subject profiles over time, and summarized by antigen, dose group, and time as means and standard deviations.

To meet the secondary objective of determining sustainability of the immune response, the subject's TACA-directed immune titer at Week 19 will be compared to her TACA-directed immune titer at Week 9. The number and percentage of subjects with a sustained immune response will be reported in the aggregate and by dose cohort if more than one dose cohort is enrolled. In addition, the ratio of week-19 and week-9 titers will be plotted as dot plots and summarized as the mean, median and range.

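### Sustained immune response is judged only from Week 19 against Week 9, with no pre-vaccination titer, cut-off or responder denominator, so the reported figure can err in either direction

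*Combined protocol and SAP*

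**What the plan says.** The sustainability paragraph of Section 12.b (Data Analysis Plan) has three parts.

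- The comparison: "the subject's TACA-directed immune titer at Week 19 will be compared to her TACA-directed immune titer at Week 9".
- The count: "The number and percentage of subjects with a sustained immune response will be reported in the aggregate and by dose cohort", the cohort breakdown applying if more than one cohort is enrolled.
- The continuous summary: "the ratio of week-19 and week-9 titers will be plotted as dot plots and summarized as the mean, median and range".

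The same section defines a positive response against the pre-vaccination titer. It is a "titer of 1:40 post-vaccination when the baseline pre-vaccination titer was 0", or an increase of at least four-fold when that titer was above 0. Section 11 calls a subject's response adequate if she has a "positive TACA-directed immune response at any one of the first five designated time points", namely Weeks 2, 3, 4, 7 and 9. Neither definition is carried into the sustainability paragraph. The next endpoint, the response to the Week-19 booster, does have an explicit threshold: more than two-fold, Week 21 over Week 19.

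**The concern.** A response is sustained only if there was one to sustain. The stated comparison starts at Week 9 and takes whatever titer is present then as its reference, whether or not vaccination induced it. Non-zero titers without vaccination are to be expected. Section 3 refers to "naturally occurring carbohydrate-reactive IgM antibodies", and the positive-response rule itself provides for a baseline above 0.

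Three groups are therefore handled badly: subjects who never responded and stay flat, subjects who responded early and were back near baseline by Week 9, and subjects who decline from a high Week-9 titer but remain clearly positive. The first two look maintained and the third looks lost.

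At stake is what the trial can say about durability, which Section 12.b treats as a secondary objective. With 3 to 6 subjects per cohort, one misclassified subject moves a cohort percentage by 33 points (1/3) or 17 points (1/6). With no cut-off stated, the definition could also be chosen after the titers are known.

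**Working it through.** The plan gives no expected rate, sample size or cut-off for this endpoint, so there is no figure of its own to reproduce. The check applies the plan's two stated operations to example titer profiles.

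**Rules, from Section 12.b**

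- Positive at week w: titer(w) of at least 40 if baseline = 0; titer(w)/baseline of at least 4 if baseline > 0. I read 1:40 as 1:40 or higher.
- Ratio: titer(Week 19)/titer(Week 9).

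**Example profiles (assumed reciprocal titers)**

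| Baseline | Weeks 2, 3, 4, 7 | Week 9 | Week 19 | Positive in Weeks 2–9? | Positive at Week 9 / Week 19? | Ratio |
|---|---|---|---|---|---|---|
| 40 | 40, 40, 40, 40 | 40 | 40 | No (40/40 = 1) | No / No | 40/40 = 1.0 |
| 20 | 40, 80, 80, 80 | 40 | 40 | Yes, from Week 3 (80/20 = 4) | No / No (40/20 = 2) | 40/40 = 1.0 |
| 20 | 20, 40, 80, 160 | 320 | 80 | Yes | Yes (320/20 = 16) / Yes (80/20 = 4) | 80/320 = 0.25 |
| 0 | 0, 0, 0, 0 | 0 | 0 | No | No / No | 0/0, undefined |

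Rows 1 and 2 have no response at Week 19 but a ratio showing full maintenance. Row 3 still meets the positive-response rule but has the lowest ratio. Row 4 has no ratio, and the plan has no rule for it.

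**Effect on a reported percentage (illustration)**

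Take nine subjects, the number Section 12.a gives for a trial with no dose-limiting toxicity (3 + 6 = 9). Because the plan has no cut-off, I assume that a ratio of at least 1 is scored as sustained. All responders are taken to be positive at Week 9, non-persisting responders have a ratio below 1, and never-responders have flat non-zero titers.

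- *Six responders, three persisting with flat titers, three never-responders.* By ratio: (3 + 3)/9 = 67%. By the positive-response rule: 3/6 = 50% of responders and 3/9 = 33% of all subjects.
- *The same nine, but the three persisting responders follow row 3.* By ratio: 3/9 = 33%, and the three counted are the never-responders. By the positive-response rule: still 3/6 = 50% of responders.
- *Three responders, none persisting, six never-responders.* By ratio: 6/9 = 67%. By the positive-response rule: 0/3 = 0%.

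The ratio-based figure is thus 17 points too high in the first case, 17 points too low in the second and 67 points too high in the third, against the responder-based figure.

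**The case against.** The strongest reply is that the plan never says a ratio of 1 counts as sustained. The ratio is introduced as an additional summary, and since a positive immune response is defined in the same section, a sustained one can be read as presupposing it. This stands in part. Never-responders *can* be counted; a reader might infer that they *would* be, and the text does not support that. But the presupposition is not written down, the only stated operation is titer against titer, and the percentage is of subjects rather than responders. All subjects with both samples also enter the ratio summary, whatever the count means.

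A second reply is that baseline-anchored positives are already reported by time point. Those reports cover Weeks 2, 3, 4, 7 and 9; Week 19 is not clearly included. Separate counts by week also do not show which subjects stayed positive.

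A third reply is that the stakes are low. Dose decisions rest on toxicity alone, Section 12.a calls the immunogenicity assessment qualitative, and sustainability is not among the secondary objectives listed in Sections 2 and 4. This limits the weight of the point, but Section 12.b still commits to reporting the percentage by dose cohort.

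A reader might also go further and argue from the skin tests. At the Week-9 visit 100 µg of "Mimotope P10s-PADRE will be given id alongside the control antigens", so one might infer that persistence is overstated or that added peptide distorts the comparison between cohorts. The documents do not support this. The plan never calls the interval antigen-free. Only the Week-9 skin test can fall between the two samples, and it is the same in every cohort. Table 1 leads from 300 µg to either 500 µg or 100 µg, so the three doses are never compared together. Nor can the effect on titer be judged: Section 6.d lists the skin-test dose without adjuvant, while Section 4.b names the adjuvanted vaccine, and those passages need reconciling.

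**Conclusion.** The point holds as a weakness of method, and more than wording is missing: the stated comparison uses the wrong reference for persistence of an induced response. It can call subjects sustained who never responded or had already lost their response, and it can miss subjects who remain positive. The error has no fixed direction. In the nine-subject illustrations it ranges from 17 points too low to 67 points too high against the responder-based percentage. Those sizes rest on the assumed titers and the assumed cut-off of 1 and are not predictions. The misclassification in the example profiles needs only the plan's positive-response rule and the ratio. The Week-9 skin test is at most a note for interpreting Week 19. Safety conclusions and dose decisions are not affected.

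**What to change.** In Section 12.b:

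1. Define a sustained response as meeting the plan's positive-response rule against the pre-vaccination titer at both Week 9 and Week 19.
2. Use as denominator the subjects positive at Week 9 who have a Week-19 sample, and state how many Week-9 responders lack that sample, since Section 12.c allows no imputation.
3. Show alongside it the number positive at Week 19 out of all Week 2–9 responders and out of all subjects.
4. Restrict the Week-19/Week-9 ratio summary to Week-9 responders, or stratify it by Week-9 response. Restriction also removes the undefined ratios, because a Week-9 responder cannot have a titer of 0. If non-responders are shown as a separate stratum, state how a Week-9 titer of 0 is handled.
5. Apply all of this separately to IgM and IgG and to ELISA and FACS.
6. When interpreting Week 19, note that a 100 µg mimotope skin test is given at the Week-9 visit in every cohort.

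The cost is analysis-plan wording. The serum samples are already scheduled. The main denominator becomes smaller, and the percentage may move up or down.
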